ROUTE OF ADMINISTRATION	Intracavernosal Injection (PRP) + extracorporeal shockwave therapy (SWT)
SUBJECT POPULATION	60 male subjects between the age of 30-75 with Mild or Mild-to-Moderate ED
STUDY OBJECTIVES	
Primary: To investigate and compare the treatment efficacy of PRP injection + SWT vs placebo injection / SHAM treatment in men with mild-moderate ED, as measured by IIEF.
 
Secondary: To study incidence of adverse events and safety of PRP injection + SWT treatment in men with mild-moderate ED, as measured by IIEF.

INVESTIGATION PLAN	
60 men with Erectile Dysfunction (ED) of organic origin, that meet all of the inclusion and none of the exclusion criteria, will be randomized to receive either PRP+SWT, or placebo/sham in a 1:1 double-blinded fashion.
 
a) Group A (30 subjects): Autologous PRP injection + SWT therapy. All subjects in this group will receive 2 sessions of autologous PRP penile injection with 30 ± 7 day treatment interval. 5mL of PRP will be injected at each session. Additionally, patients will receive a total of 3600 shocks over a five-week period, starting at initial PRP injection.
 
b) Group B (30 subjects): Placebo (Normal Saline) + SHAM. All subjects in this group will receive 2 sessions of normal saline penile injection with 30 ± 7 day treatment interval. 5mL of normal saline will be injected at each session. Additionally, patients will receive SHAM treatment over a five-week period, starting at initial placebo injection.

DURATION OF STUDY	7 months (1 month screening, 5 weeks of therapy sessions, 6 months of follow-up).

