2.4 Combination Restorative Therapy for Erectile Dysfunction

The development of ED therapeutics that focus on neurovascular regeneration and repair strategies are of great importance. A large body of *pre-clinical* work has demonstrated the effect of SWT alone (monotherapy) on angiogenesis and progenitor / stem cell recruitment for ED [2, 3, 8-11]. PRP monotherapy importantly is also supported by well-defined mechanistic insights obtained from rigorously conducted animal studies [12-19]. All the previous studies in humans have evaluated either IIEF scores and / or penile Doppler ultrasound hemodynamic parameters, but there has not been evaluation of the treatment as a combination. The proposed mechanisms of both interventions would

suggest that the combination therapy would act in a synergistic manner, with superiority over monotherapy. Success of our proposed work could fundamentally change the standard of care for ED and substantially improve the quality of life for tens of millions of men.

3. Study Objectives

3.1 Primary Objective:

To investigate and compare the safety of PRP and SWT vs placebo/sham treatment in men with mild-moderate ED.

3.2 Secondary Objective:

To study the treatment efficacy of PRP and SWT treatment vs placebo/sham treatment in men with mild-moderate ED.

4. Study Endpoints

4.1 Primary Endpoint (safety):

- Incidence of treatment emergent serious adverse events (TE-SAEs) in all patients during the study period. Adverse events will be recorded at every visit. The following contains a list of the anticipated adverse events:
 - Pain
 - Bruising
 - Swelling
 - Edema
 - Allergy
 - Penile Fracture
 - New Penile Curvature

4.2 Secondary Endpoints (efficacy):

- Change in IIEF-EF score from baseline to 3 and 6 months post-therapy compared to control group.
- Percentage of subjects that achieve minimal clinically important difference (MCID) in IIEF-EF from baseline to 3 and 6 months post-therapy compared to control group,
- Percentage of subjects who either decrease or discontinue use of PDE5i after three months post-therapy compared to control group.

4.3 Exploratory Endpoints:

- Differences in Doppler ultrasound parameters (PSV and EDV) from baseline to 6 months post-therapy compared to control group.
- Treatment satisfaction as assessed by EDITS questionnaire in all subjects.
- Changes in IPSS questionnaire between treatment and control group.
- Perceptions of therapeutic allocation between treatment and control group.

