12.2 Serious Adverse Events (SAEs)

A serious adverse event (SAE) is defined as an AE which, in the view of the Investigator results in: 1) Death; 2) a life-threatening event (i.e. an event in which the subject was at risk of death at the time of the event; it does not refer to an event which hypothetically might have caused death if it were more severe); 3) inpatient hospitalization of > 24 hours or prolongation of existing hospitalization; 4) a significant disability/incapacity; or 5) a congenital anomaly/birth defect. Other important medical events may be considered SAEs if, in the opinion of the Investigator, they jeopardize the subject or require intervention to prevent one of the other outcomes listed above. Based on prior investigations, we do not anticipate any SAEs related to the study procedures [23-26].

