14.1 Data Analysis Plan

Analysis plan: Continuous data will be analyzed using ANOVA with repeated measures, or student's T-Test (where applicable) in order to compare differences between the treatment and control groups. For categorical data, Fisher's Exact test to determine differences between groups. Statistical significance will be evaluated using $\alpha=0.05$.

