14.2 Sample Size

Inclusion Criteria are men with IIEF scores >11 which includes men with mild (IIEF 16-21) and mild/moderate (12-16) Erectile dysfunction. Minimal clinically important difference (MCID) for these groups are an increase of 2 for mild and 5 for moderate ED. Previous studies on the effect of placebo show about a 15% improvement in men with mild to moderate ED. Therefore, 15% of the placebo group is expected to meet MCID. Results from the PRP safety study by Matz et al. 2018, which showed a mean improvement in IIEF of 4.14 points in seven patients with ED after PRP. In the interventional group, we expect 50% to meet MCID. At 80% power, we will therefore need 30 patients in each group to detect a difference of 35% between treatment and placebo arms.

$$\text{Sample size} = \frac{2(Z_{\alpha/2} + Z_{\beta})^2 P(1-P)}{(P_1 - P_2)^2}$$

$$24 = (2*(1.96+0.84)^2 * (0.25*(1-0.25))) / (0.35^2)$$

Assuming attrition of approximately 20%, an additional 6 participant slots will be added to each group for a total sample size of 60 subjects.

15. Risks and Benefits

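### The primary safety endpoint is not clearly pooled or by arm, and the only test that fits it is uninformative for an event expected not to occur; no interval or precision is specified

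*Combined protocol and SAP*

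**What the plan says.** The primary objective in section 3.1 is comparative: "To investigate and compare the safety of PRP and SWT vs placebo/sham treatment in men with mild-moderate ED". The primary endpoint in section 4.1 is "Incidence of treatment emergent serious adverse events (TE-SAEs) in all patients during the study period". It names no contrast with the control arm, whereas all three secondary efficacy endpoints in section 4.2 do. The Protocol Synopsis lists the same primary endpoint but gives a different primary objective: "To investigate and compare the treatment efficacy of PRP injection + SWT vs placebo injection / SHAM treatment in men with mild-moderate ED, as measured by IIEF".

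Section 14.1 contains nothing specific to TE-SAEs. The one rule that can apply to a yes/no outcome is the one for categorical data, Fisher's "Exact test to determine differences between groups", with significance judged at alpha 0.05 and sidedness not stated. There is no confidence interval, acceptable rate, margin or safety population. Section 14.2 sizes the trial on MCID response, a secondary endpoint, and gives no power or precision for the primary one.

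On expected numbers, section 12.2 says "we do not anticipate any SAEs related to the study procedures", and section 15.1 cites no serious events in 75 men. Section 12.3 counts a serious event as a TE-SAE only if there is a reasonable possibility that the product caused it, which lowers the expected count further.

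**The concern.** Two things are unsettled about the trial's primary result. The first is what will be estimated: one rate over 60 men, half of whom receive neither PRP nor shockwave, or a rate in each arm. The second is how it will be judged. If the generic rule in section 14.1 is applied, the primary safety result is a significance test on an event expected at or near zero, in arms of 30.

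Such a test will almost always be non-significant, whether or not the combination carries a risk that matters. What 30 treated men can provide is an upper bound on the serious-event rate, and the plan does not ask for one. Without it, a report that follows the plan could state a p-value or a single rate and leave the reader unable to see how large a risk remains possible.

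**Working it through.** **Inputs.** 30 men per arm, 1:1 (sections 8 and 14.2). About 20% attrition, so 24 evaluable per arm (14.2). Fisher's exact test at alpha 0.05 (14.1). The two-sided level is inferred from the 1.96 in section 14.2. The true event rates below are assumptions, because the documents give none beyond expecting no related serious events.

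**The plan's own figure.** Section 14.2 gives "24 = (2*(1.96+0.84)^2 * (0.25*(1-0.25))) / (0.35^2"). That is 2 × 7.84 × 0.1875 / 0.1225 = 24.0 per arm, and 24 / 0.80 = 30. The arithmetic reproduces, but it concerns MCID response only.

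**Smallest significant table with no control events.** For k events against 0 in equal arms of n, the two-sided Fisher p-value is 2 × C(n,k) / C(2n,k).

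- n = 30, k = 5: 2 × 142,506 / 5,461,512 = 0.0522, not significant.
- n = 30, k = 6: 2 × 593,775 / 50,063,860 = 0.0237, significant.
- n = 30, k = 5, one-sided: 0.0522 / 2 = 0.0261, significant.
- n = 24, k = 5, two-sided: 2 × 42,504 / 1,712,304 = 0.0496, significant.

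The observed treated-arm rate must therefore reach 5/30 = 16.7%, 6/30 = 20% or 5/24 = 20.8%, depending on the reading, against zero in controls. With one control event (two-sided, 30 per arm), 7 against 1 gives p = 0.0523 and 8 against 1 gives p = 0.0257, so eight are needed.

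**Power.** If the true control rate is 0, two-sided power is P(X ≥ 6) with X binomial(30, p), or P(X ≥ 5) with X binomial(24, p).

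| True treated rate (assumed) | 30 per arm | 24 per arm |
|---|---|---|
| 5% | 0.3% | 0.6% |
| 10% | 7.3% | 8.5% |
| 15% | 28.9% | 28.7% |
| 20% | 57.2% | 54.0% |
| 25% | 79.7% | 75.3% |

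With 30 per arm, 80% power needs a true rate of about 25.5%. A true control rate of 1% lowers power further: 5.6% instead of 7.3% at a treated rate of 10%.

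**What estimation gives.** With zero events the exact (Clopper-Pearson) two-sided 95% upper limit is 1 − 0.025^(1/n).

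- n = 30: 11.6%.
- n = 24: 14.2%.
- n = 60, both arms pooled: 6.0%.

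For the difference with 0/30 in each arm, the Newcombe limit is z²/(n + z²) = 3.84 / 33.84 = 11.35%, so the interval runs from about −11 to +11 percentage points.

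**Why pooled or by arm matters.** Suppose 2 treated men and no control men have an event. The treated-arm rate is 2/30 = 6.7% (exact 95% interval 0.8% to 22.1%). The pooled rate is 2/60 = 3.3% (0.4% to 11.5%). The halving holds only when the control arm has no events.

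**The case against.** The strongest reply is that the plan nowhere says a non-significant test, or a low pooled rate, will be taken as proof of safety. A reader might infer that from a primary safety endpoint paired with a significance test, but section 14.1 names only the test and the level. This stands: misreading is a risk that the plan leaves open, not a rule it states.

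Nor do the documents establish pooling. The wording in section 4.1 may simply identify who is counted, and sections 3.1 and 14.1 both point to a comparison of groups. This also stands. Against it, the efficacy endpoints name the control group and this one does not, so the text needs clarifying.

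Pooling also has a use. Control men undergo the blood draw and a saline injection given in a similar way to PRP. For harms of these shared steps, 60 men give a tighter bound than 30 (6.0% against 11.6% with zero events). That supports a pooled rate as a supplement, but it cannot answer the section 3.1 question about PRP and shockwave. Harms of shared steps also tend to cancel in a between-arm test, which is a reason to show each arm's absolute rate.

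Finally, this is a Phase I/II pilot. Adverse events are reviewed at every visit from Day 0, and the DSMB sees them by masked group, can unmask, and can recommend termination (sections 13.4.1.2 and 13.4.1.3). Participant protection therefore does not rest on the p-value, and exact intervals could be computed later from arm-level counts. But the DSMB's safety criterion is qualitative, and nothing commits the final report to arm-level estimates.

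**Conclusion.** The concern holds in this form: the primary safety endpoint is ambiguous between a pooled and a by-arm rate, and the only applicable analysis is uninformative at the rates the protocol expects. Power is 0.3% at a true treated rate of 5% and 7% at 10%, assuming a two-sided test, 30 per arm and a true control rate of zero.

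Two figures should not be quoted without their conditions. The 6-against-0 threshold is not fixed: it assumes a two-sided test with all 30 men per arm analysed, and becomes 5 against 0 if the test is one-sided or 24 per arm are evaluable. The threshold is also an observed count, not a true rate below which detection is impossible. Likewise, the 11.6% upper limit requires all 30 treated men to be observed; with 24 it is 14.2%. None of these variations makes the test informative.

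It would go too far to say that the trial cannot compare safety at all. A by-arm description with intervals is within its reach, but the plan does not specify one.

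**What to change.** - **Section 4.1 and the Synopsis:** define the endpoint as the proportion of men with at least one TE-SAE in each arm, among all men who received any study treatment. Reconcile the Synopsis objective with section 3.1.
- **Section 12.3:** state how attribution to the product or procedures applies to men given saline and sham, so that the between-arm difference is well defined.
- **Section 14.1:** make the primary safety analysis the per-arm proportion with an exact (Clopper-Pearson) 95% confidence interval, plus the between-arm difference with a 95% interval (for example Newcombe). Any Fisher p-value is descriptive only and is not read as evidence of safety. A pooled rate may be added as a supplement.
- **Section 14.2:** state the precision. Zero events gives a two-sided 95% upper limit of 11.6% if all 30 treated men are observed, and 14.2% if only 24 are.

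The cost is a few lines of text and analysis, with no extra patients, visits or data. The downside is a more modest safety conclusion: even with no events, the trial could exclude only treated-arm rates above roughly 12% to 14%. The change should be made before the data are unblinded.

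### Five between-arm efficacy comparisons share one unadjusted 0.05 and none is named as the deciding one; the powered MCID comparison has no time point

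*Combined protocol and SAP*

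**What the plan says.** The secondary (efficacy) endpoints in Section 4.2 include "Change in IIEF-EF score from baseline to 3 and 6 months post-therapy compared to control group" and "Percentage of subjects that achieve minimal clinically important difference (MCID) in IIEF-EF from baseline to 3 and 6 months post-therapy compared to control group". A third endpoint is the proportion who reduce or stop PDE5i use after three months. Taken visit by visit, that is five comparisons between arms. Section 4.3 holds a separate exploratory tier, and none of the five is in it.

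Section 14.1 offers repeated-measures ANOVA or a t-test where applicable for continuous data, and Fisher's exact test for categorical data. It ends with "Statistical significance will be evaluated using" alpha = 0.05. It gives no lead efficacy endpoint, deciding visit, ANOVA term, test order or adjustment. The 1.96 in the Section 14.2 formula shows that the level is two-sided.

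Section 14.2 bases the sample size on MCID response alone, with 15% expected on placebo, and for the active arm: "In the interventional group, we expect 50% to meet MCID". No visit is attached to either rate.

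The documents differ on the weight of efficacy. The synopsis gives the primary objective as "To investigate and compare the treatment efficacy of PRP injection + SWT vs placebo injection / SHAM treatment in men with mild-moderate ED". Section 3.1 makes safety primary and Section 3.2 makes efficacy secondary. The primary endpoint is TE-SAE incidence in both places.

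**The concern.** The comparisons can disagree. Month 3 may differ from Month 6, and a mean change may differ from a responder rate. As written, the plan lets the efficacy conclusion rest on whichever result turns out favourable, and the error rate of that conclusion is then not the one Section 14.1 states.

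This matters more than it would for purely descriptive secondary endpoints. Efficacy is the only basis for the sample size, and Section 14.1 commits to significance testing. Section 13.4.1.3 also lets the DSMB recommend stopping for larger than expected benefit, or because a significant difference has become improbable. Neither can be judged cleanly until the comparison in question is known.

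**Working it through.** **1. The plan's own figure.** Section 14.2 writes "24 = (2*(1.96+0.84)^2 * (0.25*(1-0.25))) / (0.35^2"). This gives 2 × 2.80² × 0.1875 / 0.1225 = 2.94 / 0.1225 = 24.0 per arm, and 24 / 0.8 = 30 per arm with 20% attrition. The stated figures reproduce. They spend the full two-sided 0.05 on one MCID comparison. (The 0.25 used for P is not the mean of 15% and 50%, which is 0.325; that is a separate matter.)

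**2. Upper reference, independent tests.** The chance of at least one false positive is 1 − 0.95^k.
- k = 4: 1 − 0.8145 = 0.185
- k = 5: 1 − 0.7738 = 0.226

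These figures are too high for this trial. The endpoints are correlated, and Fisher's test is conservative: its true size at a 15% rate in both arms is 0.024 with 24 per arm and 0.017 with 30.

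**3. Simulation of the planned tests with no treatment effect.** From the documents: 24 or 30 per arm, 1:1 allocation, two-sided 0.05, MCID thresholds of 2 and 5 points, and a 15% responder rate. Assumed, because the documents give no values: correlation of 0.3 to 0.9 between the Month 3 and Month 6 changes; normal change scores with SD 5; the two thresholds in equal shares; 30% as an alternative responder rate; and a PDE5i event rate of 30%, correlated 0 or 0.4 with the changes. There were 40,000 trials per setting in the main run. The three-test row comes from separate runs.

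| Tests counted | Any false difference, either direction | Multiple of 0.05 | False difference favouring active | Multiple of 0.025 |
|---|---|---|---|---|
| Four IIEF-EF tests (two t, two Fisher) | 0.087–0.130 | 1.7–2.6 | 0.043–0.065 | 1.7–2.6 |
| All five, with PDE5i | 0.111–0.152 | 2.2–3.0 | 0.056–0.077 | 2.2–3.1 |
| One repeated-measures group term and two MCID Fisher tests, no PDE5i | about 0.07–0.09 | 1.4–1.8 | 0.034–0.044 | 1.4–1.8 |

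The last column uses 0.025 because a single two-sided 0.05 test errs in favour of active treatment at that rate. A repeat run with a different seed agreed to within about 0.006.

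**4. Which row applies.** The text does not settle it. Section 14.1 names repeated-measures ANOVA first but states no term, so one test or two on the change score are both compatible with it. The PDE5i comparison may carry no information, because Section 8.2.14 requires all participants to stop PDE5i for the whole study while Section 4.2 counts those who reduce or stop. Those two sections must be reconciled.

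**5. Power of the contrast the plan sized for.** Exact power of Fisher's test at 15% vs 50% is 0.668 with 24 per arm and 0.777 with 30. Splitting alpha costs more. On the normal-approximation calculation, 0.01 per test gives 0.505 and 0.634, and 80% power would need 41 evaluable per arm.

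**The case against.** The strongest reply is that this is a Phase I/II pilot of 60 men with a safety primary endpoint, that the efficacy endpoints are labelled secondary, and that formal familywise control over them is largely a matter of preference. Much of that stands. No section says that any single p < 0.05 establishes efficacy, so the either-direction rates describe what the plan permits and not a success rule that it declares. A full gatekeeping scheme is not required here.

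It is also fair to say that Section 14.2 points at one endpoint, MCID response, and leaves only the visit open. Testing MCID by Fisher's test at both visits gives a simulated two-sided rate of only about 0.03 to 0.05, so that ambiguity alone costs almost no alpha. The inflation comes from allowing the change score, and possibly PDE5i use, to serve as alternatives.

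Two stronger readings are tempting, and neither is supported. A reader might infer that a false claim of benefit has a probability two to three times 0.05. It does not: false results favouring active treatment come to about 0.04 to 0.06 on the four tests, and the multiple holds only against 0.025. A reader might also take the 0.19 or 0.23 from the independence formula as this trial's error rate. The planned tests are correlated and partly conservative, so those values are upper references only.

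The reply does not remove the core gap. Section 14.1 never links the powered endpoint to the efficacy conclusion, and the synopsis raises that conclusion to the primary objective.

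**Conclusion.** The concern holds as an unnamed deciding contrast with moderate error inflation. The chance of some false significant efficacy difference in either direction is about 0.09 to 0.13 on four tests, 0.11 to 0.15 on five, and 0.07 to 0.09 on the narrowest reading of Section 14.1. In favour of active treatment on four tests it is about 0.04 to 0.06, against 0.025. All these values rest on the assumed correlations, change-score distribution and event rates above, which the documents do not supply.

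The absence of a named contrast rests on the text alone and needs no assumption. The safety endpoint and its conclusions are unaffected. The change is worth making because it determines what the trial can say about efficacy and costs very little.

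**What to change.** Leave TE-SAE incidence as the primary (safety) endpoint. Before unblinding, state in Sections 14.1 and 14.2 that the single deciding efficacy contrast is MCID response, the endpoint the trial was sized for, at one named visit, by Fisher's exact test at two-sided 0.05. The sponsor chooses Month 3 or Month 6; the documents do not favour either. State that the 15% vs 50% assumption refers to that visit. Report the other efficacy comparisons as supportive, as estimates with 95% confidence intervals. Bring the objectives in the synopsis and Section 3 into line, and reconcile the PDE5i endpoint with Section 8.2.14.

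The cost is a few sentences, with no added patients, visits or data, and no larger sample on account of multiplicity. There are two downsides. A significant result on another endpoint or visit could not by itself be claimed as demonstrated efficacy. The deciding test also has about 67% power with 24 evaluable per arm and 78% with 30, not the stated 80%, and the plan should say so. A fixed test order or Holm's procedure for the remaining comparisons is optional. Under a fixed order led by this contrast, later tests would be closed about one time in three at 24 per arm (1 − 0.668 = 0.332), even if the plan's assumed effect is true.

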14.2 Sample Size

Inclusion Criteria are men with IIEF scores >11 which includes men with mild (IIEF 16-21) and mild/moderate (12-16) Erectile dysfunction. Minimal clinically important difference (MCID) for these groups are an increase of 2 for mild and 5 for moderate ED. Previous studies on the effect of placebo show about a 15% improvement in men with mild to moderate ED. Therefore, 15% of the placebo group is expected to meet MCID. Results from the PRP safety study by Matz et al. 2018, which showed a mean improvement in IIEF of 4.14 points in seven patients with ED after PRP. In the interventional group, we expect 50% to meet MCID. At 80% power, we will therefore need 30 patients in each group to detect a difference of 35% between treatment and placebo arms.

$$\text{Sample size} = \frac{2(Z_{\alpha/2} + Z_{\beta})^2 P(1-P)}{(P_1 - P_2)^2}$$

$$24 = (2*(1.96+0.84)^2 * (0.25*(1-0.25))) / (0.35^2)$$

Assuming attrition of approximately 20%, an additional 6 participant slots will be added to each group for a total sample size of 60 subjects.

15. Risks and Benefits

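### The trial is sized only on a yes/no cut of IIEF-EF, whose planned Fisher test has 67% to 78% power rather than 80%, while the IIEF-EF change already listed as an endpoint has no precedence, deciding time point or stated power

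*Combined protocol and SAP*

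**What the plan says.** The primary endpoint in Section 4.1 is the incidence of TE-SAEs. Efficacy is secondary, and Section 4.2 lists first "Change in IIEF-EF score from baseline to 3 and 6 months post-therapy compared to control group", then the percentage of men reaching the MCID at the same two times.

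Section 14.2 bases the sample size on the second of these alone. On the cut-offs: "Minimal clinically important difference (MCID) for these groups are an increase of 2 for mild and 5 for moderate ED". On the rates: "Therefore, 15% of the placebo group is expected to meet MCID" and "In the interventional group, we expect 50% to meet MCID". The conclusion: "At 80% power, we will therefore need 30 patients in each group to detect a difference of 35% between treatment and placebo arms". The formula gives 24 per arm, and 6 per arm are added for about 20% attrition.

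Section 14.1 assigns repeated-measures ANOVA or a t-test to continuous data. For the responder endpoint: "For categorical data, Fisher's Exact test to determine differences between groups". One significance level of 0.05 applies throughout. No efficacy endpoint or time point is named as deciding. No assumed difference, SD or power is given for the IIEF-EF change. The schedule in Section 8.1 collects the IIEF at screening, Month 3 and Month 6.

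**The concern.** The only efficacy comparison with a power claim reduces a numeric score to yes or no. A man who gains 1 point counts the same as one who gets worse. A man with mild ED who gains 2 points counts the same as one who gains 10. Discarding that information usually costs power, and in a trial with 24 evaluable men per arm the cost may be large. Fisher's test is also conservative at this size.

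Two things are at stake. A real effect of the assumed size could be missed on the comparison the trial was sized for. And if the responder test and the IIEF-EF change disagree, or Months 3 and 6 disagree, the plan does not say which result answers the efficacy question.

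The cut itself is also unsettled. Section 14.2 labels scores of 16 to 21 mild and 12 to 16 mild/moderate. Section 6.1 labels 12 to 21 mild to moderate and 22 to 25 mild. The cut-off that applies to a man scoring 18 or 23 is therefore unclear. The change score does not depend on this.

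**Working it through.** **Inputs.** From Section 14.2: 15% and 50%; z-values 1.96 and 0.84 (two-sided 0.05, 80% power); P = 0.25; 20% attrition; a cited uncontrolled mean gain of 4.14 points in seven men. From Section 14.1: the tests and the 0.05 level. The SD of the IIEF-EF change is not in the documents, so everything from step 3 on rests on stated assumptions.

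**1. The plan's own figure.** 2 × (1.96 + 0.84)² × 0.25 × 0.75 / 0.35² = 2.94 / 0.1225 = 24.0, and 24 / (1 − 0.20) = 30. Both reproduce. P = 0.25 is not the mean of the two rates; (0.15 + 0.50)/2 = 0.325 gives 28.1. The unpooled formula, (z-sum)² × (0.25 + 0.1275) / 0.35², gives 24.2, so 24 can be reached by a normal approximation. It is not a calculation for Fisher's test.

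**2. Power of the planned test.** Sum Bin(x; n, 0.50) × Bin(y; n, 0.15) over all tables with two-sided Fisher p ≤ 0.05:
- n = 24: 66.8%
- n = 30: 77.7%
- 80% is first reached at n = 32 (81.5%).

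This step needs no distributional assumption.

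**3. Power of a t-test on the change, under a normal shift.** Assume normal change, equal SD and one cut-off c. A 50% rate puts the active mean at c. A 15% rate puts the control mean at c − 1.036 SD. So d = z(0.50) − z(0.15) = 1.036. The noncentrality is d√(n/2).
- n = 24: 3.59, power 94.0%; gap 94.0 − 66.8 = 27.2 points
- n = 30: 4.01, power 97.7%; gap about 20 points
- 80% is first reached at n = 16 (81.0%).

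**4. Other models with the same 15% and 50%, 24 per arm** (simulation, 20,000 trials each; Fisher stays at about 66.8%):

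| Assumption | t-test power | Gap (points) |
|---|---|---|
| Half the men at each cut-off (2 and 5), SD 3 to 6 | 95–98% | +28 to +31 |
| Active SD 1.25 × control | about 88% | +21 |
| Active SD 1.5 × control | about 79% | +12 |
| Heavy tails, t with 4 df | about 83% | +16 |
| Heavy tails, t with 3 df | about 75% | +9 |
| 42–84% of active men shifted by 3 to 1.2 SD | 81–90% | +14 to +23 |
| Some active men moved from below the cut into the control arm's upper tail, the rest unchanged | about 54% | −13 |

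**5. The cited 4.14 points.** Take it, as an assumption, to be the between-arm difference. For the Fisher column, apply the same shift with control mean 0 and half the men at each cut-off.

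| Assumed SD | t-test, 24/arm | t-test, 30/arm | Fisher, 24/arm |
|---|---|---|---|
| 4 | 93.9% | 97.6% | 63.6% |
| 5 | 80.2% | 88.4% | 46.7% |
| 6 | 64.8% | 74.8% | 34.6% |
| 7 | 51.8% | 61.5% | 26.5% |
| 8 | 41.9% | 50.4% | 20.9% |

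**The case against.** Three stronger readings are tempting, and the documents support none of them.

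*That the plan's rates by themselves imply a 27-point gain.* Two rates do not fix a mean difference. The same 15% and 50% gave gaps from −13 to +31 points in step 4, so even the sign depends on the model. The normal shift also has an awkward consequence: with half the men at each cut-off, holding control at 15% implies a control mean change of about 0 at SD 3, −0.9 at SD 4 and −2.9 at SD 6. Section 14.2 speaks of improvement on placebo. The larger SDs therefore do not sit well with the stated rates.

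*That the full-scale score goes unanalysed.* It is the first-listed secondary endpoint and has tests assigned to it. Nothing in the plan declares the responder rate decisive.

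*That the trial's primary question is underpowered.* Sections 3.1 and 4.1 make safety primary in a Phase I/II pilot, although the synopsis lists efficacy as its primary objective. The point concerns a secondary comparison.

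A further objection is that at 4.14 points and an SD of 6 or more, the t-test falls below Fisher's 66.8%. That sets one effect against another. Under the same 4.14-point shift, Fisher falls further, to 34.6% at SD 6. What stands is that high power for the change score cannot be taken for granted.

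A responder rate is also easier for patients to interpret, and it can be the better test if benefit is all-or-none. Both are reasons to keep it as a supportive analysis.

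**Conclusion.** The point holds in a conditional form.

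Firm, from the plan's own figures: the only efficacy power claim belongs to the MCID comparison, and with the named test it is 66.8% at 24 evaluable per arm and 77.7% at 30, not 80%. Also firm: the IIEF-EF change has no precedence, deciding time point or stated power.

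Conditional: under a normal shift with equal SD and one cut-off, testing the change gains 27 points at 24 per arm and 20 at 30. The gain is smaller with heavy tails or unequal SDs. It reversed in one of the subset-benefit models tried, while the other subset models still favoured the t-test.

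This is worth changing, but it does not invalidate the trial. It affects a secondary objective, and the data needed are already scheduled.

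**What to change.** - **Sections 4.2 and 14.1:** keep TE-SAE incidence as the primary endpoint. Name the between-arm difference in IIEF-EF change at one pre-specified time point as the single key efficacy analysis, at two-sided 0.05, and state which of the two listed methods delivers it. Report the MCID responder percentages by arm as supportive, with their difference and 95% CI.
- **Section 14.2:** restate the power of the Fisher comparison as about 67% (24 per arm) to 78% (30 per arm). Add the power for IIEF-EF change at 24 and 30 per arm over an assumed range of mean difference and SD. For example, 4.14 points taken as the between-arm difference with SD 4 to 8 gives 94% to 42% at 24 per arm and 98% to 50% at 30.
- **Sample size:** leave at 60.

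The cost is a few sentences, with no new patients, visits or data. There are two small downsides. A mean difference is less directly interpretable than a responder rate, which the supportive table offsets. And the SD has to be assumed, which is why a range should be shown.
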